5.8.1 Overall Survival

Kaplan-Meier curves will be constructed to estimate overall survival probabilities. A multivariate Cox regression model for the risk of death will be developed to estimate hazard ratios for the CHARM risk groups after adjustment for baseline characteristics as described above.

5.8.2 Development/Progression of Frailty (DPF)

Frailty will be summarized at each time point using descriptive statistics. Incidence of DPF up to 1 year will be estimated with 95% confidence intervals using the cumulative incidence estimate, treating death prior to DPF as a competing event. A multivariate Cox regression model for the cause-specific hazard of DPF will be fit to estimate hazard ratios of the CHARM risks groups after adjustment for baseline characteristics as described above. Additionally, we will develop a separate Cox model using individual predictors rather than the overall CHARM score in order to assess the relative importance of the predictors in Table 5.9.1 on DPF and compare to CHARM predictive power for DPF.

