2.2.3 Secondary Objectives

To assess the ability of the composite health model to predict the following secondary outcomes at 1 year:

1. Overall survival
2. Cumulative Incidence of Frailty
3. Cumulative incidence of disability
4. Cumulative incidence of admission to a skilled nursing facility

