5. HRQOL
6. Cumulative incidence of serious organ toxicity by day 100
7. Cumulative incidence of acute grade 2-4 GVHD at 100 days, 6 months and 1 year and chronic GVHD requiring treatment with systemic immune-suppression at 6 months and 1 year
8. Survival after development of acute grade 2-4 GVHD
9. Cognitive decline at day 100

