5.8 Analysis of Secondary Endpoints

Three risk groups will be formed, based on the tertiles of the CHARM risk score. We will provide univariate summaries of each of the secondary outcomes by CHARM score risk group for each endpoint. We will then compare the risk groups multivariate models developed for each outcome separately as detailed below. All the demographic and baseline characteristics described in section 5.6 above will be considered via stepwise variable selection for inclusion in the model. Assuming an overall type I error of 10%, a significance level of 1% will be used for all secondary analyses based on Bonferroni adjustment since we will be considering 10 endpoints between section 5.8.1 and 5.8.9. A sensitivity analyses will also be done base on the CHARM score as a quantitative measure rather than tertile groups.

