5.8.8 Chronic GVHD

Incidence of chronic GVHD up to 1 year will be estimated with 95% confidence intervals using the cumulative incidence estimate, treating death prior to chronic GVHD as a competing event. A multivariate Cox regression model for the cause-specific hazard of chronic GVHD will be developed to estimate hazard ratios of the CHARM risk groups, after adjustment for baseline characteristics.

5.8.9 Serious Organ Toxicities by Day 100

Serious organ toxicities identified for this study (see Table 2.6.9) will be tabulated by type of toxicity. Number of toxicities and number of patients experiencing toxicities will be described for the first 100 days, as well as the cumulative incidence of any serious organ toxicity by day 100, with death as a competing risk. The CHARM risks groups will be compared for their association with incidences of serious organ toxicities.

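### Secondary objectives ask CHARM to predict cumulative incidence of frailty, disability, facility admission and GVHD, but the adjusted time-to-event comparisons are cause-specific hazard ratios only; an adjusted incidence comparison should be added

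*Protocol*

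**What the plan says.** Section 2.2.3 opens the secondary objectives with "To assess the ability of the composite health model to predict the following secondary outcomes at 1 year". The list includes "Cumulative Incidence of Frailty", "Cumulative incidence of disability" and "Cumulative incidence of admission to a skilled nursing facility". Objective 7 adds "Cumulative incidence of acute grade 2-4 GVHD at 100 days, 6 months and 1 year", and chronic GVHD needing systemic immunosuppression at 6 months and 1 year.

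Section 5.8 plans univariate summaries of every secondary outcome by CHARM tertile. It continues: "We will then compare the risk groups multivariate models developed for each outcome separately as detailed below". All secondary analyses use a 1% level (10% over 10 endpoints).

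For frailty the model is "A multivariate Cox regression model for the cause-specific hazard of DPF will be fit to estimate hazard ratios of the CHARM risks groups". Sections 5.8.3 (disability), 5.8.4 (first facility admission) and 5.8.7 (acute GVHD) name the same kind of model, and for chronic GVHD section 5.8.8 says "A multivariate Cox regression model for the cause-specific hazard of chronic GVHD will be developed to estimate hazard ratios of the CHARM risk groups". Death is named as the competing event in 5.8.2, 5.8.3, 5.8.7 and 5.8.8. Section 5.8.4 does not name it, although a cause-specific hazard implies a competing event.

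Section 5.7.1 builds CHARM from a Cox model for the cause-specific hazard of non-relapse mortality (NRM).

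**The concern.** With a competing event, cumulative incidence depends on two hazards: that of the event and that of the competing event. A score that raises both can show a cause-specific hazard ratio above 1 while the proportion affected by one year is equal, or even lower, because more of the high-risk group die before the event can occur. CHARM is designed to separate fatal risk, so this is a foreseeable situation here.

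At stake is what the trial may say about objectives 2, 3, 4 and 7. A hazard ratio alone could be read as showing that more high-risk subjects become frail or disabled by one year when the proportions hardly differ. Section 1.8 intends the tool for counselling older patients and families, and that use needs the proportion affected.

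**Working it through.** **Inputs from the protocol**
- One-year survival by age band, Table 5.9.2: 63%, 61%, 57%, 57%, with N = 1617, 1817, 704, 81. Weighted: (1617×63 + 1817×61 + 704×57 + 81×57)/4219 = 257,453/4219 = 61.0%, so about 39% die by one year.
- Day-100 survival, same table: 88%, 87%, 84%, 81%. Weighted: 366,072/4219 = 86.8%, so about 13% die by day 100.
- N = 880, or about 293 per tertile. The plan's own level reproduces: 10%/10 = 1%.

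**Assumptions (not in the protocol)**
- Constant hazards; no censoring before one year; no allowance for visit-based ascertainment.
- One-year mortality in the low and high tertiles of 30% and 48%, or 25% and 53%. Each pair averages 39%.
- Event hazard in the low tertile (l) of 0.3 to 0.9 per year.

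**Formula.** With death hazard d = −ln(1 − mortality), the one-year cumulative incidence is l/(l+d) × (1 − exp(−(l+d))). The break-even hazard ratio is the cause-specific ratio that makes the two tertiles' incidences equal.

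**One-year break-even ratio**

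| Mortality, low vs high | d, low / high | l = 0.3 | l = 0.6 | l = 0.9 |
|---|---|---|---|---|
| 30% vs 48% | 0.357 / 0.654 | 1.16 | 1.18 | 1.20 |
| 25% vs 53% | 0.288 / 0.755 | 1.26 | 1.30 | 1.33 |

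A different parametrisation (death hazard ratio of 1.5 to 3 between outer tertiles, scaled to 39% mortality overall, l from 0.3 to 1.2) gives 1.11 to 1.45.

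**Incidence and test statistics at l = 0.6.** For the hazard, z = ln(HR)/√(1/e₁ + 1/e₂), with e = 293 × incidence. For incidence, z is that of a difference of two proportions. Power is at two-sided 1%.

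| Mortality | Cause-specific HR | Incidence, low vs high | z, hazard (power) | z, incidence (power) |
|---|---|---|---|---|
| 30% vs 48% | 1.0 | 38.6% vs 34.2% | 0 | −1.1 |
| 30% vs 48% | 1.5 | 38.6% vs 45.7% | 3.2 (about 72%) | 1.7 (about 20%) |
| 25% vs 53% | 1.0 | 39.8% vs 32.9% | 0 | −1.7 |
| 25% vs 53% | 1.5 | 39.8% vs 44.0% | 3.2 (about 72%) | 1.0 (about 6%) |

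**How extreme are the mortality contrasts?** Take NRM as 22 of the 39 points (section 5.5) and assume the hazard of the remaining deaths is equal across tertiles. The total hazard is −ln(0.61) = 0.494, and the non-NRM share is 0.494 × 17/39 = 0.215.
- 25% vs 53%: NRM hazards 0.288 − 0.215 = 0.072 and 0.755 − 0.215 = 0.540, a ratio of about 7.5.
- 30% vs 48%: 0.357 − 0.215 = 0.141 and 0.654 − 0.215 = 0.438, a ratio of about 3.1.

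(The differences use unrounded hazards.) The milder contrast is the more cautious basis.

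**Day 100.** With assumed day-100 mortality of 9% vs 17%, or 8% vs 18.7%, and low-tertile incidence of 20% to 50%, the break-even ratio is 1.05 to 1.08.

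**The case against.** Cause-specific Cox regression accompanied by cumulative incidence curves is a coherent way to handle competing risks, and the protocol uses the same pairing for its primary endpoint. The synopsis words the secondary objective as association, which a cause-specific hazard ratio answers directly. This stands, and it is why the hazard models should remain.

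Much of the incidence information will also be visible. Section 5.8 promises summaries by CHARM group, and sections 5.8.2, 5.8.3, 5.8.7 and 5.8.8 specify cumulative incidence with confidence intervals and death as competing event. Section 5.8.1 models all-cause death by CHARM group. Disability has a further adjusted comparison of mean score among the living (5.8.3), and facility admission a rates/means model (5.8.4). What remains missing is an adjusted comparison on the scale that section 2.2.3 names, and a model of death before each event.

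A reader might infer that the hazard comparison is wrong and that the 1% test should move to cumulative incidence. The protocol does not support that. It calls no single model decisive, and an incidence test has its own difficulty: with a cause-specific ratio of 1.0 and a death hazard ratio of 3 (event hazard 0.7), simulation finds significantly lower incidence in the high-risk group in 32% of runs, only because more of that group die first. Which scale to test is a trade-off.

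A reader might also take 25% versus 53% mortality as the expected case, or apply the one-year figures to early acute GVHD. The first needs an NRM hazard ratio near 7.5 under the assumption above. For the second, the divergence at day 100 is small.

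**Conclusion.** The concern holds as a mismatch between objective and adjusted analysis for frailty, disability, first facility admission, and acute and chronic GVHD. It does not reach overall survival, cognitive decline or quality of life, and section 5.8.9 names no hazard model for organ toxicity.

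Its size is moderate. On the milder contrast, a cause-specific hazard ratio up to about 1.2 can go with no increase in the one-year proportion affected. A ratio of 1.5 still corresponds to higher incidence in the high-risk group, but with a much weaker signal. This rests on constant hazards and assumed mortality contrasts: the protocol does not say how far CHARM separates death before these events. The direction does not depend on those values: under constant hazards, the break-even ratio exceeds 1 whenever the high-risk group has the higher death hazard.

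This is an inexpensive improvement to a valid plan. It does not invalidate the planned secondary analyses.

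**What to change.** For frailty, disability, first facility admission and GVHD, chiefly at 6 months and 1 year:

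1. Keep the cause-specific hazard ratios.
2. Add an adjusted comparison of CHARM groups on cumulative incidence at the times stated in section 2.2.3, by pseudo-value or Fine-Gray regression, with death as the competing event. State that competing event for facility admission too. Section 5.8.7 currently estimates acute GVHD only to 180 days, so it would need extending to reach the one-year time point.
3. Report the CHARM effect on the hazard of death before the event.
4. Base any statement that CHARM predicts cumulative incidence on the incidence-scale result.

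The cost is protocol wording and one more regression per endpoint, plus the death-before-event model, on data already collected; the sample size does not change. The downside is two effect measures to explain side by side, including that lower incidence in the high-risk group may reflect earlier death.

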5.8.3 Development/Progression of Disability (DPD)

Incidence of DPD up to 1 year will be estimated with 95% confidence intervals using the cumulative incidence estimate, treating death prior to DPD as a competing event. A multivariate

Cox regression model for the cause-specific hazard of DPD will be developed to estimate hazard ratios for the CHARM risk groups after adjustment for baseline characteristics. Available disability scores for survivors at specific time points will be summarized using means and standard deviations. Patterns of missing disability score over time will be examined using graphical techniques and logistic regression models. At each time point, the effect of CHARM risk group and other baseline covariates on the mean disability score conditional on being alive at that time point will be estimated using the inverse probability of censoring-weighted generalized estimating equations with independent working correlation model of Kurland and Heagerty.⁶⁴ Multiple imputation methods may also be used. Additionally, we will develop a separate Cox model using individual predictors rather than the overall CHARM score in order to assess the relative importance of the predictors in Table 5.9.1 on DPD and compare to CHARM predictive power for DPD.

5.8.4 Admission to a Skilled Nursing Facility

Cumulative incidence of the time to the first facility admission will be described, along with the number of facility admissions per person years of follow up. Time to first admission will be modeled using Cox regression for the cause-specific hazard of admission, in order to compare hazard ratios between CHARM risk groups after adjustment for baseline characteristics. A multivariate proportional rates/means model⁶⁵ for the rate of facility admission accounting for multiple admissions will be estimated after adjustment for baseline characteristics, in order to estimate the relative intensities of facility admissions between the CHARM risk groups

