2.6.4 Facility Admissions

Subjects will be asked about admission to skilled facilities inclusive of nursing-homes and rehabilitation. This will cover the prior 3 months on days 100 and 180 and the prior 6 months at baseline and day 365.

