3.2.4 Facility Admission

Facility admission will include any overnight stay in a skilled nursing facility outside of the hospital. Facilities include rehabilitation, subacute rehabilitation and nursing-homes. Generally, such admissions occur as discharges from the hospital setting. Residing at home with a nurse or paid caregiver would not be considered a facility admission. Transfer of care to a rehabilitation center within the same hospital or organization would also be considered a facility admission for

the purpose of the protocol as this implies the subject was not well enough to live independently. The study chairs should be contacted to reconcile ambiguities.

Facility admission will be measured for the prior 3 months at day 100 and day 180 and the prior 6 months at day 365. The cumulative incidence of first admission to a facility as well as the rate of admissions accounting for recurrent admissions will be calculated over one year.

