4.2.5 Subject-reported data capture

At the time a subject enrolls in the study, the CIBMTR Survey Research Group (SRG) is notified and then adds that subject to CIBMTR's electronic Subject Reported Outcomes (ePRO) system for data collection tracking.

Pre-transplant subject-reported data will be collected by the center electronically or on paper forms within 21 days prior to the start of conditioning. If conditioning is delayed, the subject-reported surveys should be repeated so they are within 21 days of start of conditioning. Electronically collected pre-transplant instruments will be directly entered in the ePRO system via unique links. The center will securely email or fax pre-transplant instruments completed on paper to the SRG to enter into their electronic ePRO system. Along with the pre-transplant instruments, the center will complete the required forms in FormsNet prior to the 100 day visit so that the SRG can reach the subject for all post-transplant time points.

The SRG will administer the 100 day, 180 day and 365 day instruments online, or on paper if requested by the subject. The SRG will first confirm each subject's clinical status with the transplant center because reporting of deaths may lag. The SRG will then contact the subject via email, phone or mail to collect the subject reported information online or on paper. The SRG will follow-up with non-responders to minimize missing forms. Data will continue to be collected even if the subject has relapsed disease and/or undergone treatment for relapse to the extent feasible.

- 100 days -14/+21 days
- 180 days +/- 28 days
- 365 days +/- 28 days

At the conclusion of each subject reported data collection, subjects will be reminded of the next date of contact. The SRG will notify the transplant center if a subject's contact information has changed or if they find through follow-up that the subject has died, and centers will be required to update and enter Rave forms accordingly.

4.2.6 Quality Control:

This protocol includes tools that must be administered by a health care team member (e.g., research coordinator, nurse etc.) such as walk speed, grip strength and cognition. Standardized administration of these tools across sites will reduce measurement error and improve generalizability of results. Therefore, site staff administering these tests will be required to attend mandatory training. Video training will also be made available to view. A log of trained users

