The following table lists all subject reported assessments to be collected, including the number of items and estimated time to complete at each time point. This appendix also includes all items/questions included on each subject reported assessment. For some assessments, language has been modified to fit administration electronically or on paper, as opposed to in person. Any modifications are noted in the below sections.

| Study Assessments / Testing | # of items | Minutes | Baseline (≤21 days Pre-conditioning) | Day 100 -14/+21 | Day 180 +/- 28 | Day 365 +/- 28 |
|---|------------|---------|--------------------------------------|---------------------|----------------------|----------------------|
| Karnofsky performance status by subject | 1 | <1 | X | X | X | X |
| Facility admissions | 1-3 | 1 | | X | X | X |
| PROMIS Depression | 4-12 | 1-2 | X | X | X | X |
| PROMIS Anxiety | 4-12 | 1-2 | X | X | X | X |
| PROMIS Physical function | 4-12 | 1-2 | X | X | X | X |
| OARS IADL | 6 | 2 | X | X | X | X |
| Falls | 1 | <1 | X | X | X | X |
| Frailty phenotype: Weight loss | 2 | <1 | X | | X | X |
| Frailty phenotype: Exhaustion | 5 | 2 | X | | X | X |
| Frailty phenotype: Activity level | 6-18 | 2-5 | X | | X | X |
| Number of medications for polypharmacy | 4 | 1 | X | | | |
| Race/ethnicity, education, income, demographics | 6 | 2 | X | | | |
| Total time for Subject reported outcomes | | | 13-20 minutes | 7-10 minutes | 11-17 minutes | 11-17 minutes |

Race/ethnicity, education, income, demographics

1. What is the highest grade you finished in school?

- 1-8 grades
- 9-11 grades
- High school graduate
- Some post-college work
- Some college
- Junior college degree
- College degree (BA/BS)
- Advanced degree

2. What is your marital status?

- Single, never married

- Married
- Separated
- Divorced
- Widowed

3. What is your current employment status? (please choose all that apply)

- Employed 32 hours a week or more
- Employed less than 32 hours a week
- Full-time student
- Part-time student
- Homemaker
- On medical leave
- Disabled
- Unemployed
- Retired
- Other

4. What is your race? (please select all that apply)

- White
- Asian
- Black or African-American
- Native Hawaiian or Other Pacific Islander
- Native Indian or Alaskan Native
- Don't know

5. What is your ethnicity?

- Hispanic or Latino
- Not Hispanic or Latino
- Don't know

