 - with some help (*can do light housework but need help with heavy work*); or
 - are you completely unable to do any housework?
6. Can you take your own medicines...
- Without help (*in the right doses at the right time*);
 - With some help (*able to take medicine if someone prepares it for you and/or reminds you to take it*); or
 - Are you completely unable to take your medicines?
7. Can you handle your own money...
- Without help (*write checks, pay bills, etc.*);
 - With some help (*manage day-to-day buying but need help managing your checkbook and paying your bills*); or
 - Are you completely unable to handle money?

Falls in past 6 months

Question has been modified from text box, to multiple choice response in order to control data entry in electronic format.

1. How many times have you fallen in the last 6 months?
- 0 times
 - 1 time
 - 2 times
 - 3 or more times

Facility admissions

At day 100 and 180

1. Have you been admitted to a skilled nursing facility in the last 3 months? This would include an acute rehabilitation facility, nursing-home, or sub-acute rehabilitation. Do NOT include admissions to the hospital.

- Yes
- No
- unsure

At day 365

1. Have you been admitted to a skilled nursing facility in the last 6 months? This would include an acute rehabilitation facility, nursing-home, or sub-acute rehabilitation. Do NOT include admissions to the hospital.

- Yes
- No
- unsure

Frailty phenotype: Weight loss*

Questions have been modified for electronic and paper administration during which patient may not be able to self-weigh or recall exact previous weights. Also modified to remove “Refused” response item, as patients may skip question to refuse.

At Pre-HCT

1. To the best of your knowledge, have you lost or gained weight over the past year?

- Yes
- No
- Don't know

2. [if yes] Did you lose or gain weight because you were trying to, or not (For example, by dieting or exercising)?

- Tried to
- Did not try to
- Don't know

Frailty phenotype: Exhaustion*

Questions have been modified to remove “Refused” response item, as patients may skip question to refuse.

* <https://www.johnshopkinssolutions.com/solution/frailty/>

* <https://www.johnshopkinssolutions.com/solution/frailty/>

1. In the past month, on average have you been feeling unusually tired during the day?

- Yes
- No
- Don't know

2. If yes, have you been feeling unusually tired:

- All of the time
- Most of the time
- Some of the time
- Don't know

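### Facility admissions are seen only inside the fixed recall periods of answered surveys, but Section 5.8.4 relates them to person-years of follow-up, so numerator and denominator cover different time

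*Protocol*

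**What the plan says.** Protocol Section 5.8.4 plans the cumulative incidence of first facility admission, "along with the number of facility admissions per person years of follow up", a Cox model for first admission, and a proportional rates model for repeated admissions by CHARM risk group. Section 3.2.4 sets the period: the cumulative incidence "as well as the rate of admissions accounting for recurrent admissions will be calculated over one year".

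The data come from the subject. Section 2.6.4 states: "Subjects will be asked about admission to skilled facilities inclusive of nursing-homes and rehabilitation". Table 4.2.4 marks the item as subject report. Section 3.2.4 fixes the recall: "Facility admission will be measured for the prior 3 months at day 100 and day 180 and the prior 6 months at day 365". Appendix 4 words the item accordingly: "Have you been admitted to a skilled nursing facility in the last 3 months" at days 100 and 180, and "Have you been admitted to a skilled nursing facility in the last 6 months" at day 365. The answers are yes, no or unsure, with no count and no date. The Appendix 4 table lists one to three items for this topic, yet only one is printed, although the appendix says of itself: "This appendix also includes all items/questions included on each subject reported assessment".

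Surveys need not fall on the nominal day. Section 4.2.5 allows "100 days -14/+21 days" for the first and 28 days either side for the other two, that is days 86–121, 152–208 and 337–393. Section 2.6.8 lists what the post-transplant CIBMTR forms supply. Facility admission is not among it, and no second source is named.

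**The concern.** An admission can enter the numerator only if it falls inside the recall period of a survey that was answered. Follow-up for survival comes from the clinical forms and continues whether or not a survey is answered. If person-years of follow-up means time alive on study, time nobody asked about is treated as admission-free.

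Three things lower the rate: gaps between recall periods, missed surveys, and deaths before the next survey. One raises it: an admission on a day covered by two surveys can be reported twice. Nothing in the protocol says how any of these is handled for this endpoint.

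Admission to a skilled facility is a named secondary objective (Section 2.2.3) and part of the study hypothesis (Section 2.2.1). A statistical analysis plan could redefine the denominator, but it cannot recover days that the protocol's own instrument never asks about.

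**Working it through.** The protocol states no expected admission rate and no survey response rate, so there is no figure of its own to reproduce.

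**Inputs.** Recall of 3, 3 and 6 months (Section 3.2.4), taken as 91, 91 and 182 days. Survey windows from Table 4.2.1 and Section 4.2.5. The year is days 0 to 364.

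**1. Nominal dates, all surveys answered.** Recall covers days 9–99, 89–179 and 183–364.
- Recalled days: 91 + 91 + 182 = 364
- Asked twice: days 89–99 = 11
- Asked at least once: 364 − 11 = 353
- Never asked: 365 − 353 = 12 (days 0–8 and 180–182)

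**2. Nominal dates, one survey missed.**
- Day 100 or day 180 missed: covered 91 + 182 = 273; unasked 365 − 273 = 92 days (25% of the year)
- Day 365 missed: covered days 9–179 = 171; unasked 365 − 171 = 194 days

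**3. Limits of the visit windows.**
- A day-121 survey reaches back only to 121 − 91 = day 30.
- A day-393 survey reaches back to 393 − 182 = day 211. After a day-152 survey the gap is 211 − 152 = 59 days.
- A day-152 survey reaches back to 152 − 91 = day 61. After a day-121 survey the overlap is 121 − 61 = 60 days.

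**4. Visits uniform over the windows, survivors to day 365, full response.** Some recalled days fall outside the year:
- After day 365, on average 28² / (2 × 56) = 7.0 days
- Before day 0, on average 5² / (2 × 35) = 0.4 days

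Recalled days inside the year: 364 − 7.0 − 0.4 = 356.6, and 356.6 / 365 = 0.977. A simulation of 20,000 sets of visit dates splits this into 0.908 of the year asked at least once and 0.069 asked twice; 0.908 + 0.069 = 0.977. At constant risk the rate is therefore about 2% low if both reports count and about 9% low if duplicates are removed.

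**5. Adding missed surveys** (an assumed share missed at each time point, survivors only):

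| Missed | Asked at least once | Asked twice | Sum | Low, de-duplicated | Low, overlaps count twice |
|---|---|---|---|---|---|
| 0% | 0.908 | 0.069 | 0.977 | 9% | 2% |
| 10% | 0.822 | 0.055 | 0.877 | 18% | 12% |
| 20% | 0.736 | 0.044 | 0.780 | 26% | 22% |
| 30% | 0.652 | 0.034 | 0.686 | 35% | 31% |

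**6. Adding deaths.** Overall survival in Table 5.9.2, weighted over the four age groups, is 86.8% at day 100 and 61.0% at 1 year. A simulation used this survival, visits spread over the windows, recall of 91.3 and 182.6 days, and an assumed constant 0.1 to 0.3 admissions per person-year. The ratio of the observed rate to the true rate was:
- Full response: 0.83 de-duplicated, 0.89–0.90 with overlaps counted twice
- 20% missed: 0.67–0.68 and 0.72

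Scoring each survey as yes or no, as in the printed item, gives 0.85–0.88 and 0.68–0.71, because several admissions in one recall period count as one.

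**7. Direction.** If 50% to 80% of admissions are assumed to fall in days 20–120, with yes/no scoring, full response and no deaths, the ratio is 1.03–1.05, slightly high. With deaths added it is 0.95–0.98.

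**The case against.** The strongest objection concerns direction. A reader might infer that the gaps and overlaps alone bias the rate low. They do not: on nominal dates 12 unasked days stand against 11 double-asked days, and early clustering of admissions can tip the rate slightly high. The full-response figure of 9% holds only if duplicates are removed. This objection stands. The downward pull comes mainly from missed surveys and from deaths before the next survey.

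A reader might also infer that the plan divides by all person-years. Section 5.8.4 does not say so. Follow-up is undefined there, and an analysis plan could restrict it. For frailty and disability, Sections 3.2.2 and 3.2.3 censor subjects who miss assessments; Section 3.2.4 has no such sentence. The objection stands as to the denominator, but no definition of exposure fills in days that were never asked about.

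Finally, a reader might infer that the CHARM comparison is attenuated. The rate per person-year is descriptive, and the models estimate hazard ratios and relative rates, in which similar under-coverage across groups largely cancels. Shrinkage needs non-response or early death to differ by CHARM group. That is plausible for a score meant to predict mortality, but the protocol gives no figure for it.

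Two lesser points also stand. Exact 91-day edges are a modelling choice, since subjects will not recall to the day. And Section 3.2.4 says most admissions follow hospital discharge, so the first few days after transplant may carry little risk. On the other side, Section 2.4.8 explains the same 3-month recall for weight loss as covering the time since the previous assessment. A fixed length does not achieve that once visits move within their windows or a survey is missed.

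**Conclusion.** The mismatch is real: numerator and denominator cover different time, and the protocol does not reconcile them. At full response among survivors the net error is near zero, about 2% low or about 9% low depending on how overlaps are treated. With an assumed 20% of surveys missed it is roughly 22% to 26% low among survivors, and lower still once deaths are counted.

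These sizes rest on uniform visit dates, constant admission risk, follow-up time read as time alive on study, and response rates that the protocol does not give. An effect on the CHARM comparison is conditional, not shown. The point concerns one secondary endpoint and leaves the primary analysis untouched. It is a cheap improvement.

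**What to change.** In Sections 2.6.4 and 3.2.4, Table 4.2.4 footnote 5 and Appendix 4, replace the fixed post-transplant recall for facility admissions. At the first answered survey ask about admissions *since your transplant*; after that ask about admissions *since your last completed survey on [date]*. Record the number and dates of admissions, because the printed yes/no/unsure item cannot feed a recurrent-event model or date a first admission.

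In Section 5.8.4, state that the denominator of the rate, and the time at risk in the models, is the person-time covered by answered surveys, with each day counted once.

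This closes gaps and overlaps up to the last completed survey, and the next answered survey recovers a missed one. Time between the last survey and death stays unobserved, but it no longer counts as admission-free.

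The cost is a change of survey wording, one or two extra items and one sentence in the analysis section. The downside is longer recall for subjects who missed a survey.
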